- 4) The inter-individual variation in fat use will be determined by observing the range of whole-body fat use estimates at rest and during exercise recorded after controlling for intra-individual variability / calculated measurement error.

Ethical Considerations / Potential Risks and Discomfort

Skeletal muscle and Adipose Tissue Biopsies: The main ethical issues anticipated relate to the relatively invasive optional skeletal muscle and adipose tissue samples to be acquired at Visit 4. However, as noted, both of these biopsies are optional and thus, participants will be freely able to choose whether or not to have these procedures. The skeletal muscle and adipose tissue biopsies will be obtained to look at associations between fat use at visit 2 and 3, and characteristics of these tissues obtained at Visit 4 (e.g. content and activity of proteins involved in substrate metabolism, skeletal muscle fibre composition and mitochondrial content, location and function). Both techniques are well established procedures in Human Physiology research and are regularly performed in the physiology laboratories at the University of Bath. Only

minor complications are typically observed (such as bleeding from the skin wound, bruising and minor soreness over the days afterwards). For example, the minor complication rate was reportedly 0.15% when using the Bergstrom muscle biopsy technique [78]. Participants will be fully explained the risks associated with the procedures and are provided with an extensive guide (included with the participant information sheet) to help manage these issues if opted for. These sheets also list the possible complications which are more severe (e.g. intramuscular bleeding, denervation or infection) although these complications are fortunately very rare and risks are further minimised by following best practice. All procedures will be performed only by trained individuals to minimize any risk and the minimum amount of each tissue will be taken to minimise discomfort whilst gaining the maximum information to answer the research questions.

Anaesthetic: The use of anaesthetic for muscle and adipose tissue biopsies may cause possible side effects including allergic reactions, heart arrhythmia and nausea. However, the initial health screen will be individually checked by a doctor, who will sign a Patient Specific Direction (PSD) to prescribe the anaesthetic for the procedure. A patient information leaflet with further information regarding the anaesthetic will also be included in the participant information sheet.

Dual-energy x-ray absorptiometry (DEXA) Scan: A DEXA is a non-invasive technique that uses a very low exposure to radiation. While DEXA was primarily designed to measure bone mineral density, a secondary application offered is a precise estimate of total and localized body composition. The radiation dose is often compared to the small exposure experienced during a short flight (e.g. London to Paris), and a tiny fraction [1/30th] of the amount of radiation experienced during a typical chest x-ray. This technique is routinely used in hospitals and with elite athletes but nonetheless this does represent some exposure to a small amount of radiation. The risks associated with this amount of radiation are described as ‘trivial’ (less than 1 in a million per whole body scan). This information will be included in the personalised feedback provided to participants which would not normally be available to them. The exposure of ionising radiation from the DEXA Scan has been reviewed and a declaration made by both a lead Medical Physics Expert ([name]) and a lead Clinical Radiation Expert ([name]).

Cardiac Event: The incremental graded cycling test to volitional exhaustion (FAT_{MAX} Test), which is performed twice in the study, once at Visit 2 and once at Visit 3, is associated with an

increased risk of a cardiac event. The American College of Sports Medicine [79] report an incident rate of approximately 6 cardiac events per 10,000 tests. This small risk is likely further lowered in individuals with no current or history of cardio-pulmonary or metabolic disease, or family history of cardiac events. This test is central to the aims of the study and all sessions will be closely supervised by first-aid and CPR trained staff. Participants will have the option to freely stop at any stage in the incremental graded cycling tests, further reducing the risk of any cardiac event.

Blood Sampling: Two x approximate 10 mL fasting blood samples across the study will be taken via venepuncture (one at Visit 2 and one at Visit 3). These procedures are associated with a small risk of infection, embolism or haematoma. Further, these procedures can also cause minor bruising and skin irritation. However, the occurrence of such events is very rare and risks are further minimised by our strict adherence to best practice.

Urine Sampling: Two x approximate 10 mL urine samples will be collected across the study (one at Visit 2 and one at Visit 3). This will involve the collection of urine in sealed disposable containers and storage in a fridge until analysis. The samples will be analysed immediately after taken on Visit 2 and Visit 3 with the clinical waste produced disposed as outlined below.

Clinical Waste: As biological samples are being collected, clinical waste will be produced and must be handled appropriately to minimise the risk of injuries and contamination. All contaminated equipment (e.g. needles, syringes, urine sample collection containers) will be immediately disposed of in clinical waste bins or follow strict adherence to ‘cleansing protocols’ outlined in the Standard Operating Procedures developed by the Department for Health, University of Bath. The clinical waste bins will be sealed (with autoclave) and collected by a member of staff in the Department for Health, University of Bath, before being incinerated in accordance with COSHH policies.

Importantly, risk assessments have been performed and standard operating procedures designed by the Department for Health, University of Bath, are in place for all above procedures and will be strictly adhered to.

Time commitment and inconvenience: Participants will be asked to visit the University of Bath four times (Visit 1 will take approximately 45 minutes, Visit 2 and 3 will take approximately 90 minutes, and Visit 4 will take a maximum of 60 minutes [if both muscle and adipose tissue biopsies are opted for]). Testing will take place after fasting for 12-hrs at a time in the day most suitable for the participant (subject to availability of research team and lab

facilities). Additionally, for lifestyle analysis, participants will be asked to wear a physical activity monitor(s) and fill in a self-weighted diet diary during the 7-days before Visit 2 and Visit 3. Participants will also be asked to replicate their diet and physical activity for at least 48-hrs prior to Visit 2 and Visit 3. For some people this may be seen as an inconvenience, however, participants will be provided with personalised feedback on their habitual activity and diet, which would not normally be available to them.

Consent Issues: Only persons who are capable of understanding the nature of the trial and what it entails will be included in this study (no vulnerable individuals will be included). Even if a person gives written consent to take part in this study they will be made fully aware that they are free to withdraw from the study at any time without giving any explanation. All participants will be fully briefed regarding the nature and risks of all procedures, which are central to the research questions, both verbally and in writing before providing consent to take part in the study.

Data and Sampling Handling / Confidentiality: As personal identifiable data is being collected there is a small risk to participant confidentiality. This will be addressed by generating a unique subject code that will be used on all stored data and samples collected, making it completely anonymous. Furthermore, all hardcopies of identifiable information will be stored in a locked filing cabinet in a secure office on the University of Bath Main Campus. All electronic data / record files will be stored on the University of Bath's secure server, involving a password-protected user log-on and inaccessible to anyone outside of the research team. All biological samples will be stored at -80 degrees C in the Department for Health Physiology laboratory. This laboratory is alarmed and access is limited to the research group. Any published data will be completely anonymised. All personal data and biological samples will be destroyed at the end of the study (defined as 5 years after the completion of the final subject, by which time all analysis must be finished and any remaining samples destroyed). White blood cells from the blood sample (extracted from the buffy coat layer and collected for the isolation of DNA), skeletal muscle samples and adipose tissue samples will be stored under the authority / via approval from the NHS HRA South West – Central Bristol Research Ethics Committee. y held by).

Participant Withdrawal: Participants are freely able to withdraw from the study at any time without providing reasons for doing so and without any prejudice. Participants can withdraw through contacting any member of the research team. If a participant withdraws one month

[figure not shown]
after their completion of the study, it may not be possible to withdraw their individual data as some results may already have been published. This is clearly explained on the participant information sheet and as all data will be anonymised, no individual results will be identifiable in any way.

Advertisement for Study Recruitment: Participants will be recruited through advertising the study using posters, local press (radio and newspaper advertisements), online social media platforms (twitter, facebook, callforparticipants) and the University of Bath website. The poster will be displayed throughout the University of Bath and the local area and with appropriate permission, in other prominent locations (e.g. local sport and fitness centres, community centres, hospitals and GP practices).

Expenses: Participants will receive a free of charge parking permit for the days they are required to visit the University.

Conflicts of Interests: There are no conflicts of interest for this study.

Any adverse events relating to the study procedures will be documented and followed up until the event is either resolved or adequately explained.

[figure not shown]

Figure 1. Study Outline and approx. Timelines

[figure not shown]
[figure not shown]

Figure 2. Study Schematic

	Stage 1	Stage 2	Stage 3	Stage 4	Stage 5	Stage 6	Stage 7	Stage 8	Stage 9	Stage 10	Stage 11	Stage 12	Stage 13	Stage 14
Time (mins)	0 - 4	4 - 8	8 – 12	12 – 16	16 – 20	20 – 24	24 – 28	28 – 30	30 - 32	32 – 34	34 – 36	36 – 38	38 – 40	40 – 42
Applied Mass (kg)	1	1	1.1	1.1	1.5	1.8	2.1	2.7	3.4	4.0	4.6	5.3	5.9	6.6
RPM	30	40	60	80	80	80	80	80	80	80	80	80	80	80
Proposed Watts	30	40	65	90	115	140	165	215	265	315	365	415	465	515
Actual Watts	29.440	39.254	64.769	86.359	117.762	141.314	164.867	211.972	266.927	314.032	361.137	416.092	463.197	518.153
Applied Mass (kg) required for proposed watts	1.019	1.019	1.104	1.146	1.465	1.783	2.102	2.739	3.375	4.012	4.649	5.286	5.923	6.560

Figure 3. FAT_{MAX} Protocol One

	Stage 1	Stage 2	Stage 3	Stage 4	Stage 5	Stage 6	Stage 7	Stage 8	Stage 9	Stage 10	Stage 11	Stage 12	Stage 13	Stage 14
Time (mins)	0 - 4	4 - 8	8 – 12	12 – 16	16 – 20	20 – 24	24 – 28	28 – 30	30 - 32	32 – 34	34 – 36	36 – 38	38 – 40	40 – 42
Applied Mass (kg)	1	1.1	1.1	1.5	1.8	2.1	2.4	3.1	3.7	4.3	5.0	5.6	6.2	6.9
RPM	40	60	80	80	80	80	80	80	80	80	80	80	80	80
Proposed Watts	40	65	90	115	140	165	190	240	290	340	390	440	490	540
Actual Watts	39.254	64.779	86.359	117.762	141.314	164.867	188.419	243.375	290.480	337.584	392.540	439.645	486.750	541.705
Applied Mass (kg) required for proposed watts	1.019	1.103	1.146	1.464	1.783	2.101	2.420	3.057	3.693	4.330	4.967	5.604	6.241	6.878

Figure 4. FAT_{MAX} Protocol Two

References

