Visit 2 and 3 (Main Trial Days; approx. 90 minutes)

Preliminary Main Trial Day Lifestyle Measurements:

For the 7-days prior to Visit 2 and at least 2-days prior to Visit 3, the participant will be instructed to:

- Wear a physical activity monitor (Actiheart™)
- Complete a self-weighed diet diary (this includes at least 3 week-days and at least 1 weekend day prior to Visit 2, and the immediate 48-hrs prior to the beginning of each main trial day)
- Record step count via a provided pedometer or personal device (e.g. mobile phone app)

This is to assess participant's physical activity levels, energy expenditure and energy / macronutrient intake. Participants will be asked to replicate their physical activity levels and diet 48-hrs prior to the beginning of each main trial day (Visit 2 and 3). Additionally, they will be asked to avoid any vigorous physical activity for the prior 48 hrs and avoid alcohol consumption for the prior 24 hrs to the beginning of each main trial day.

Main Trial Days:

Visits 2 and 3 are identical. For both of the main trial days, participants will be asked to arrive at the laboratory after fasting for 12 hrs (\pm 1 hr). The main trial days can take place either in the morning or afternoon, but must be at the same time of the day (\pm 1 hr) and must take place within 7-28 days of each other. The main trial days will follow the below protocol:

- i. Upon arrival to the laboratory, participants will be asked to provide an approximate 10 mL urine sample and void.
- ii. Anthropometric measurements (body stature (cm), weight (kg), and waist and hip circumference (cm)) will then be assessed.

- iii. After a brief period of rest in a semi-supine position in a resting laboratory, 4 x 5-min resting expired gas samples will then be collected into Douglas Bags to determine resting metabolic rate and substrate use at rest via indirect calorimetry. The International Physical Activity Questionnaire (IPAQ) will also be completed during the initial brief resting period.
- iv. A 10 mL blood sample will then be taken via venepuncture for analysis of metabolites and hormones involved in substrate metabolism, and genotyping.
- v. After the 10 mL blood sample, the maximal incremental graded cycling test to volitional exhaustion (FAT_{MAX} test) will be completed (see below for the protocol).

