Once the FAT_{MAX} test is finished, the main trial day is complete. If this is the first main trial day (Visit 2), participants will then complete the above protocol 7-28 days later. Participants will be asked to maintain their habitual lifestyle between Visit 2 and 3.

Visit 4 (approx. 50 minutes)

Visit 4 will take place between 2 – 7 days after Visit 3. Participants will be asked to arrive to the laboratory after a 12-hr fast at a similar time of the day to visit 2 and 3 (\pm 1 hr), at least 48-hrs after Visit 3 and having consumed 568 mL of plain water upon waking. Additionally, the participant will be asked to avoid any vigorous physical activity and alcohol consumption for the prior 24 hrs to the beginning of this Visit. After voiding, a dual energy X-ray absorptiometry (DEXA) scan will be performed to assess body composition. After the scan, the **OPTIONAL** skeletal muscle and / or fat biopsy will then be taken (see below for the skeletal muscle and adipose tissue sampling techniques). Once this visit is finished, the participant's involvement in the study is complete. I

Study Participants:

We plan to recruit a total of 200 male and female adults who are 'healthy' or 'at risk of developing metabolic disease'. Participants will be recruited from within the University of Bath and the surrounding areas by email, online and social media platforms (Twitter, University of Bath webpage and callforparticipants.com), poster advertising and word of mouth.

The inclusion criteria is:

- Male or Female
- Aged between 18 – 65 years

- No current or previous history of known cardio-pulmonary, metabolic or musculoskeletal disease
- A body mass index (body mass in kilograms divided by height in metres squared) between 18.9 and 35 kg/m².
- All physical activity / fitness levels
- Willingness and sufficiently able to meet the study demands (including the preliminary main trial day measurements and procedures, and maintain their habitual lifestyle (physical activity and diet) across the main study period [Visit 1 to Visit 4]).

Exclusion criteria:

- Taking any medication that may influence study parameters (lipid and / or carbohydrate metabolism)
- Any reported use of substances, other condition, or behaviour deemed either to pose undue personal risk to the participant, or introduce bias into the experiment.
- Any bleeding disorder or taking any medication which impacts blood coagulation
- Any female who is breast-feeding or may be / is pregnant

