- Individuals with radio-opaque implants (such as a knee or other joint replacement) or medical devices (such as a pacemaker)

Additional exclusion criteria for individuals who opt in for the optional skeletal muscle and / or adipose tissue biopsy are:

- Known tendency towards keloid scarring
- Known sensitivity or allergy to any local anaesthetic medicines

Study Methodology:

Questionnaires

Participants will complete several questionnaires throughout the study as outlined under 'Study Design' (please see the enclosed documents outlining each questionnaire). These consist of:

- a) Health History questionnaire (completed by all participants)
- b) Physical activity readiness questionnaire (PAR-Q; completed by all participants)
- c) Lidocaine Administration Health Questionnaire (to be completed by participants who opt for the muscle and / or adipose tissue biopsy)

- d) Participant Questionnaire (Age, sex, ethnicity, smoking status, dietary patterns / special dietary requirements; completed by all participants)
- e) Self-reported Menstrual Cycle / Reproductive Status (Females only)
- f) Long Form International Physical Activity Questionnaire (IPAQ; [69])

Diet Assessment

In an attempt to standardise upon commencement of trials and analyse potential associations with study parameters, participants' energy and macronutrient intakes will be assessed via a self-weighed diet diary in the 7 days prior to Visit 2 and 3. This must include at least 3 weekdays, at least 1 weekend day and the immediate 48-hrs prior to visit 2. Participants will be asked to replicate their diet for 48-hrs prior to each main trial day (i.e. Visit 2 and 3). For Visit 4 participants will be asked to record their evening. Participants will be provided with a set of digital weighing scales (Pro Pocket Scale TOP2KG, Smart Weigh Scales) to accurately weigh food and energy-containing drink products. Diet records will be analysed to estimate energy and macronutrient intakes (Nutritics Ltd., Dublin, Ireland). These diaries will additionally be used to assess study / standardisation compliance.

Physical Activity / Energy Expenditure Assessment

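### Preparation for tissue sampling at Visit 4 is looser than for the fat-use measurements it is compared with, so some tissue associations may partly reflect recent exercise or diet

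*Combined protocol and SAP*

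**What the plan says.** **Visits 2 and 3 (fat use).** Under Preliminary Main Trial Day Lifestyle Measurements, "they will be asked to avoid any vigorous physical activity for the prior 48 hrs and avoid alcohol consumption for the prior 24 hrs" before each main trial day. Participants also replicate diet and physical activity over the preceding 48 h. The Physical Activity / Energy Expenditure Assessment section adds a step count as a practical marker of adherence, and says that unmet activity standardisation could invalidate results.

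**Visit 4 (tissue).** The Visit 4 section says "the participant will be asked to avoid any vigorous physical activity and alcohol consumption for the prior 24 hrs". The participant arrives after a 12-h fast, at a similar time of day, "at least 48-hrs after Visit 3 and having consumed 568 mL of plain water upon waking". On spacing, "Visit 4 will take place between 2 – 7 days after Visit 3". No diet or activity replication, activity monitor or step count is stated. The Diet Assessment section has one incomplete sentence about recording the evening before Visit 4.

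**Who takes part.** The inclusion criteria in Study Participants admit all activity and fitness levels, and require habitual diet and activity to be maintained from Visit 1 to Visit 4.

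**What the tissue is for.** Ethical Considerations says that the biopsies serve to examine "associations between fat use at visit 2 and 3, and characteristics of these tissues obtained at Visit 4". The biopsy procedure sections list fibre type, intramyocellular lipid, gene expression, and protein content and activity. Item 2 of Statistical / Data Analysis correlates each variable with fat use and passes the significant ones to a hierarchical regression. It names no term for recent exercise, recent diet or time since the Visit 3 test.

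**The concern.** The two sides of each tissue association are measured in differently controlled states. If that difference were the same for everyone, or random, it would do little harm: a common shift leaves a correlation unchanged and random variation weakens it somewhat.

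Here it need not be random. The plan lets participants follow their habits until 24 h before biopsy, and habits differ systematically. Recent vigorous exercise is then likely to track habitual activity and cardiorespiratory fitness, both of which the introduction lists as influences on fat oxidation. A tissue measure that responds to exercise over a day or two could correlate with fat use because both follow training habits, and be reported as a determinant. Unreplicated diet could act in a similar way.

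What is at stake is the interpretation of the tissue part of Objective 2. The primary outcome, the body-composition comparison and the reliability objectives do not depend on Visit 4 preparation.

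**Working it through.** The plan gives no figure to reproduce on this point. The check sets the timing rules side by side and then asks how large the effect could be under stated assumptions.

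**1. Timing rules**

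| | Before Visits 2 and 3 | Before Visit 4 |
|---|---|---|
| No vigorous activity | 48 h | 24 h |
| No alcohol | 24 h | 24 h |
| Diet and activity replicated | 48 h | not stated |
| Step or activity record | yes | not stated |
| Fast | 12 h | 12 h |
| Gap after the previous exhaustive test | 7 to 28 days (Visit 2 to Visit 3) | 2 to 7 days, at least 48 h |

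The unprotected window is 48 − 24 = 24 h: self-chosen vigorous exercise between 24 and 48 h before biopsy, plus unreplicated diet. The Visit 3 test falls outside that window because of the 48-h minimum.

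**2. The 2 to 7 day interval after the Visit 3 test**

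Assumptions: true tissue-to-fat-use r = 0.30; interval t uniform on 2 to 7 days; residual effect m·exp(−t/τ), with m = 0.5 or 1 SD and τ = 1, 2 or 4 days. The documents give no value for r, m or τ.

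- *Interval unrelated to fat use.* The largest SD of the residual effect is 0.123 (m = 1, τ = 4), so r becomes 0.30/√(1 + 0.123²) = 0.298. Simulation with 400,000 draws gives 0.298 to 0.302 across all settings, within its Monte Carlo error of about 0.0014 per value.
- *Size of the response also rising with fat use, by 30% to 50% per SD.* Observed r is 0.303 to 0.312 for τ = 1, 0.318 to 0.357 for τ = 2, and 0.347 to 0.444 for τ = 4.

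The interval alone is therefore close to harmless. Material bias from it needs both slow decay and a response tied to fat use, and the documents establish neither.

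**3. Exercise in the unprotected window**

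Take a marker with no true link to fat use. Let v be the share of its variance due to recent state, and ρ the correlation of that state with fat use. The spurious correlation is r = √v × ρ. The chance of passing the P < 0.05 screen uses Fisher's z: the test statistic is centred on atanh(r)·√(n − 3). All values of v, ρ and n are assumed; the plan states no number of biopsies.

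| v | ρ | r | n = 50 | n = 100 | n = 200 |
|---|---|---|---|---|---|
| 0.1 | 0.1 | 0.03 | 5.5% | 6% | 7% |
| 0.2 | 0.3 | 0.13 | 15% | 26% | 47% |
| 0.4 | 0.3 | 0.19 | 26% | 47% | 77% |

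For the middle row, √0.2 × 0.3 = 0.134; at n = 100, 0.135 × √97 = 1.33, and P(Z > 1.96 − 1.33) is about 26%. The nominal rate is 5%. The figures run from negligible to substantial and, where ρ is not zero, rise with n. They describe the unadjusted screening step only.

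**4. Noise alone**

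If state is unrelated to fat use, a true correlation shrinks by √(1 − v): 0.95, 0.89, 0.84 and 0.77 for v = 0.1, 0.2, 0.3 and 0.4. These are upper limits on what better preparation could recover, since matched rules would not remove all state variance.

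**The case against.** A reader might infer that the exhaustive test at Visit 3 contaminates the biopsies. The documents do not support that. Visit 4 is at least 48 h later, as long as the vigorous-activity limit the study accepts before measuring fat use, and no section says how long exercise alters any tissue measure. Calling mRNA, enzyme activity or intramyocellular lipid state-sensitive is a judgement, and fibre type is plausibly less exposed.

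The confounding route is also partly covered. Habitual activity (chest-worn monitor, IPAQ) and VO2peak are measured, and if they correlate with fat use they enter the hierarchical regression. The 12-h fast at a similar time of day limits acute dietary variation. Replicating diet repeats each person's own intake, so differences between people remain; its clearest purpose is to make two trial days comparable. Time since the last vigorous session will partly stand in for habitual activity, so forcing it into every model would cost precision in a subsample of unstated size. Biopsies are optional, the study is exploratory, and tissue characteristics are secondary.

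Most of this stands, and it lowers the severity and rules out mandatory covariates. It does not close the gap. Entry of activity and fitness into the regression depends on a significance screen, and neither measures exercise in the two days before biopsy. The plan gives no reason for the looser rule, and recent exercise that is not recorded at the time cannot be reliably recovered later.

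**Conclusion.** The point holds in limited form. Visit 4 preparation is looser than Visit 2 and 3 preparation in two respects: 24 h rather than 48 h without vigorous activity, and no stated replication or record of diet and activity. Because compliance permits recent training that is likely to differ by habitual activity, associations of the more state-sensitive tissue measures with fat use may partly reflect recent exercise or diet.

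The size is not established. Under the assumptions shown, a spurious r lies between about 0.03 and 0.19 before any adjustment, and adjustment for habitual activity and fitness would remove part of it. The stronger statement that the tissue associations do carry exercise effects goes beyond the documents. Minor severity; a cheap improvement.

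**What to change.** 1. For biopsy volunteers, reconcile the Visit 4 preparation with the study's own Visit 2 and 3 standardisation, or state why it differs. The existing 48-h minimum after Visit 3 means that alignment would not require moving the visit.
2. At Visit 4, record hours since the Visit 3 test, hours since the last vigorous session, and diet and steps over the preceding 48 h. Complete the unfinished sentence in Diet Assessment.
3. Prespecify a sensitivity analysis of the tissue associations adjusted for time since last vigorous exercise, alongside habitual activity and fitness, and report it next to the main result. For volunteers with no vigorous session after Visit 3, the two recorded times coincide, so only the time since last vigorous exercise should enter the model.

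**Cost.** If the rules are aligned, volunteers accept one more day of activity restriction; in any case they keep a short diet and step record. The adjusted model loses some precision. No extra visit, procedure or participant is needed. The records must be in place before sampling.
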